Study Summary

Title:	Interstitial Fluid Pressure Estimation in Breast Cancer using 3D Subharmonic Signals from Contrast-enhanced Ultrasound
Précis:	Breast cancer patients scheduled for a breast biopsy will undergo 3D Contrast-Enhanced Ultrasound (CEUS) exam with a Logiq E9 or E10 scanner (GE Healthcare, Milwaukee, WI) using the ultrasound contrast agent Definity (Lantheus Medical Imaging, Billerica, MA). After CEUS, the measurements of interstitial fluid pressure (IFP) in the tumor and its surrounding tissue (i.e., two sites) using an intra-compartmental pressure monitoring system (Stryker, Newbury, Berkshire, UK) will be performed guided by conventional ultrasound.
Objectives:	
Primary: To determine if the pressure estimates from 3D Subharmonic Aided Pressure Estimation (SHAPE) technique is correlated with the direct measurements of IFP in breast tumors and the surrounding tissue
 
Secondary: To determine if the pressure estimates from 3D SHAPE technique have diagnostic information to detect the malignancy of breast tumors

Population:	
The patient population of this study will reflect the demographics of female breast cancer incidence in the city of Philadelphia. The overall demographics include 30% Caucasian, 29% African American, 20% Asian, and 21% Hispanic patients.
 
The sample size of this study was determined to be 25 subjects as a pilot study requiring invasive pressure measurements. The patients enrolled in this project will be female over the age of 21 scheduled for a breast biopsy. The exclusion criteria include patients with known hypersensitivity or allergy to any component of Definity as well as patients with unstable cardiopulmonary conditions or respiratory distress syndrome.

Phase:	Pilot
Number of Sites:	One; Thomas Jefferson University
Description of Intervention:	
Patients will first undergo baseline ultrasound imaging. B-mode measurements and sweeps of breast tumor in the transverse and sagittal planes will be acquired. Following baseline imaging, patients will have an administration of ultrasound contrast agent.
 
The ultrasound contrast administration will be an intravenous infusion of 2 vials of Definity/50ml saline will be administered as an IV infusion via a peripheral vein (preferably the antecubital vein), with

infusion rates of 4 to 10 ml/min (titrated to effect) through an 18-22 gauge angiocatheter. During the contrast infusion, 3D CEUS data will be collected.

Study Duration: 15 months

Participant Participation Duration: The participation duration is about 80-90 minutes (including 30 minute-long monitoring time) in a single visit.

Estimated Time to Complete Enrollment: 15 months

Schematic of Study Design:

Prior to
Enrollment

Total 25: Obtain informed consent. Screen potential subjects by inclusion and exclusion criteria; obtain history, document.

Visit 1
On the day
Of a Biopsy

Conventional ultrasound imaging will be performed to examine the tumor followed by CEUS exam. Before collecting CEUS data, Definity will be administered IV and the acoustic settings will be optimized using a built-in software in a modified Logiq E9 or E10 scanner. The 3D SHAPE data will be collected using the determined acoustic settings during the infusion. Then, we wait for the clearance of Definity and another set of SHAPE data will be collected without Definity keeping the same acoustic settings.

The subject will have local anesthesia procedure and IFP will be measured from the breast tumor and its surrounding tissue using an 18G single-use needle connected to Stryker pressure monitoring system. The measurement procedure will be guided by ultrasound imaging. The measurements will be documented as well as their locations.

Compare the results from 3D
SHAPE data to IFP measurements
and find the correlation

1 Introduction

1.1 Background Information

It has been shown that solid tumors have higher interstitial fluid pressure (IFP) compared to normal tissue. Proliferating tumor cells produce solid stress that compresses blood and lymphatic vessels causing vessel leakiness and lack of functional lymphatics. As a result, IFP becomes significantly elevated in solid tumors [Fukumura et al. 2007, Milosevic et al. 1999]. A study showed that solid tumors had higher IFP compared to normal tissue by 10-25 mmHg using mice with four human tumor cell lines [Stohrer et al. 2000]. Nathanson et al. [1994] measured IFP in the operating room in 25 patients undergoing excision breast biopsy under local anesthetic for diagnostic purposes. They found that invasive ductal carcinomas' mean IFP was 29 mmHg, while those of normal breast tissue, benign tumor, noninvasive carcinomas, and tumor with other benign breast conditions were between -0.3-3.6 mmHg. Additionally, increased IFP prevents an effective uptake of therapeutic agents and reduces the efficacy of cancer therapy [Heldin et al. 2004]. Patients with high IFP had a greater chance to recur after radiotherapy and die of progressive disease than those with low IFP [Milosevic et al. 2001]. Also early decreases in IFP during chemotherapy were highly correlated with late decreases in breast tumor volume in an animal study [Ferretti et al. 2009]. Thus, it can be clinically helpful to measure IFP in breast cancer patients.

1.2 Rationale for the Proposed Study

The IFP of breast tumors can be directly measured invasively using a wick-in-needle (WIN) technique, which employs a catheter connected to a transducer to record the pressures [Taghian et al. 2005]. However, this invasive method is difficult to apply in patients and not standard of care. Contrast-enhanced ultrasound (CEUS) has shown potential to estimate tumor IFP in animals [Halldorsdottir et al. 2014]. CEUS utilizes microbubbles, which not only enhance the backscattered signals, but at higher acoustic pressures also act as nonlinear oscillators producing multiple harmonics of the fundamental frequency. Microbubbles can also act as pressure sensors, due to the difference in compressibility between the bubble and the surrounding medium. Our group has developed the fundamental concept of subharmonic (half of fundamental frequency) aided pressure estimation (SHAPE) using CEUS and demonstrated its potential to non-invasively measure IFP [Halldorsdottir et al. 2014]. The SHAPE method estimates IFP using the inverse relationship between the CEUS signal magnitude at the subharmonic frequency and IFP. This inverse relationship varies with the applied acoustic pressure and an individual optimization of the acoustic setting for SHAPE is therefore needed [Shi et al. 1999]. Recently, we conducted a pilot study of 3D SHAPE's ability to monitor treatment response in women undergoing neoadjuvant chemotherapy (NAC) for locally advanced breast cancer (LABC) [Nam et al. 2017], showing that the subharmonic signal difference in the tumor relative to the normal tissue could predict treatment response after administration of 10% of therapy regimen (i.e., 1 cycle of neoadjuvant regimen). This study did not measure IFP directly, therefore the correlation between IFP and subharmonic signal magnitude has not been studied yet. Thus, in this

study, we will determine if the 3D SHAPE can estimate IFP in breast tumors and the surrounding normal breast tissue noninvasively.

1.3 Correlative Studies

Non-invasively, diffusion-weighted MRI and dynamic contrast-enhanced (DCE) MRI have been suggested as alternative methods for estimating tumor IFP [Hompland et al. 2014]. However, this technique has not been widely adopted in the clinic. Moreover, MRI is expensive and may not be tolerated by all patients, including those with claustrophobia, metal implants, and compromised renal function.

1.4 Potential Risks and Benefits

This study is composed of two parts: Contrast Enhanced Ultrasound (CEUS) with ultrasound contrast agent Definity and invasive Interstitial Fluid Pressure (IFP) measurements using Stryker compartment pressure monitoring system (Kalamazoo, MI).

1.4.1 Potential Risks

Serious cardiopulmonary and allergic reactions including fatalities have occurred during or following administration of Definity. However, these occurrences have been rare (less than 1 in 50,000 patients). As a result, patients with unstable cardiopulmonary conditions will be excluded. The majority of adverse events from Definity were mild to moderate in severity. Transient side effects that have been described as possibly related to Definity administration include headache (2.3%), back and renal pain (2.1%), flushing (1.1%) and nausea (1.0%). Hypersensitivity reactions to perflutren may occur, although extremely rare.

In a meta-analysis (which included 110,500 patients) [Khawaja et al. 2010] performed early after the FDA safety alerts in 2007, the incidence of serious allergic and anaphylactoid reactions immediately after the ultrasound contrast agent administration was estimated at 0.009% and 0.004%, respectively. These very rare but severe allergic reactions are secondary to a recently described variant of the type1 hypersensitivity reaction known as Complement Activation Related Pseudo Allergy, or CARPA reactions. [Szebeni 2005].

In a retrospective multicenter study, Wei et al [2008] reported on the safety of Definity (n=66164 doses) and Optison (n=12219 doses)- these included >10000 doses administered to critically ill patients in the intensive care unit or to patients with presumed ischemic chest pain. Severe reactions likely attributable to the contrast agents occurred in 8 patients (0.01%), and 4 of these were anaphylactoid reactions. Interestingly, all of the severe reactions occurred in outpatients, indicating that the FDA warning on contrast administration in patients with severe cardiopulmonary conditions likely would not have mitigated risk in these patients.

CARPA reactions may be mild to moderate (sneezing, tingling sensation, urticaria, or pruritis) or severe (wheezing, angioedema, cyanosis, and anaphylactic shock). CARPA

reactions seem more common when a large bolus of lipid shelled contrast agent is injected, and slow continuous infusions of diluted contrast likely afford significant protection against these reactions.

The use of an intravenous needle and the fluids given through the needle may cause minor discomfort, bleeding under the skin (bruise), fainting, and possible infection at the site of needle insertion. These risks are minimized by having nursing staff trained in placing IV lines perform these procedures in a safe, aseptic manner. The subjects' alternative is not to participate in this study and have only their scheduled clinical procedure(s) performed.

The invasive pressure measurement procedure (with 18G needle) has low risk similar to a stereotactic breast biopsy (mostly with 14G or larger needles). The risks includes: bruising and swelling of the breast, infection of the measurement site, and soreness at the needle injection. Also, there is low risk of infection and pain and they could be minimized by strict sterile technique and local lidocaine infiltration, respectively. The subjects' alternative is not to participate in the study.

1.4.2 **Benefits**

We do not expect any direct benefit for subjects enrolled in this study. The long-term benefits of this study will be the development of a noninvasive, safe, accurate IFP estimator. Additionally, it may lead to a novel functional predictor of malignancy in breast tumors.

2 **Study Objectives**

2.1 **Objectives**

This study is designed to compare the direct measurements of IFP in the breast tumor and its surrounding tissue with the values obtained from 3D SHAPE data (i.e., CEUS data).

2.1.1 **Primary**

The primary objective of the study is to determine if the 3D SHAPE results can be used to estimate IFPs in breast tumor and its surrounding tissue.

2.1.2 **Secondary**

The secondary objective of the study is to determine if the malignancy of breast tumor can be predicted by the 3D SHAPE results.

2.2 **Endpoints/Outcome Measures**

2.2.1 **Primary**

A Pearson's correlation coefficient above 0.5 will be considered a successful outcome.

2.2.2 Secondary

We will use the results from the biopsy as the reference standard. The significance level of Generalized linear mixed logistic or GEE logistic modeling as well as the Mann-Whitney or Student's t-test will be 0.05.

3 Study Design

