3.2 Number of Participants

We plan to enroll 25 participants.

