11.2 Analysis Plans

Radio frequency (RF) data from 3D SHAPE will be transferred to a PC for off-line analysis. 3D RF data from SHAPE will be composed of multiple 3D volumes (5 to 21 volumes) over time. Each 3D volume will consist of multiple 2D data sets (about 79 slices), which will be collected in the elevational direction. All data processing will be

performed using Matlab (R2015b; Mathworks, Natick, MA). Two regions of interest (ROI) will be selected in each elevational plane for SHAPE: one within the tumor and the other in the surrounding tissues (available top and/or bottom region of tumor). The ROIs of the tumor and surrounding area will be selected as a free form on the images generated from RF data (i.e., raw data before post-processing for on-screen display). The ROIs will be selected by the sonographer or radiologist. Then, a Fast Fourier Transform will be computed for each A-line within the ROI to obtain the frequency spectrum. The maximum magnitude from the resultant frequency spectrum will be extracted from each pre- and during infusion data sets and the ratio will be calculated for each ROI. If both top and bottom regions are selected as a surrounding area ROI, then the ratios will be averaged to one value. Finally, the obtained subharmonic signal ratios from the tumor and the surrounding area will be compared to the direct IFP measurements. Pearson's correlation coefficients will be computed between SHAPE results and direct IFP measurements by Stryker compartment pressure monitoring system. These data will also be rigorously analyzed for agreement using Bland-Altman analysis (Bland & Altman, 1999) among tumor and healthy tissue samples. To explore if the relationship between SHAPE results and IFP is confounded by or might depend on study variables collected (e.g.'s, patient characteristics, tissue/tumor characteristics, etc.) linear mixed effects or generalized estimating equations modeling will be used. Generalized linear mixed logistic or GEE logistic modeling of tumor vs. non-tumor samples will be used to explore the potential for using SHAPE results as a novel functional predictor of breast tumor malignancy. Additionally, the subharmonic signal ratio from the tumor will be used to predict the malignancy of breast tumor using a biopsy result as a gold standard. The Mann-Whitney or Student's t-test will be performed depending on the distribution of the results.

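### The secondary aim is to predict malignancy, but the plan never estimates how well SHAPE separates malignant from benign tumors

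*Combined protocol and SAP*

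**What the plan says.** The aim is diagnostic wherever it is stated. The Study Summary gives it as "To determine if the pressure estimates from 3D SHAPE technique have diagnostic information to detect the malignancy of breast tumors". Section 2.1.2 reads "The secondary objective of the study is to determine if the malignancy of breast tumor can be predicted by the 3D SHAPE results". Section 11.1 repeats the idea as the secondary hypothesis, and 11.2 says that "the subharmonic signal ratio from the tumor will be used to predict the malignancy of breast tumor using a biopsy result as a gold standard".

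In 2.2.2 the endpoint has two sentences. The first is "We will use the results from the biopsy as the reference standard". The second is "The significance level of Generalized linear mixed logistic or GEE logistic modeling as well as the Mann-Whitney or Student's t-test will be 0.05".

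Section 11.2 supplies two analyses. For the tumor ratio against biopsy: "The Mann-Whitney or Student's t-test will be performed depending on the distribution of the results". For the regression: "Generalized linear mixed logistic or GEE logistic modeling of tumor vs. non-tumor samples will be used to explore the potential", the potential in question being that of SHAPE as a predictor of malignancy.

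Section 3.2 sets the size: "We plan to enroll 25 participants". Section 11.3 justifies that number for the primary correlation only.

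**The concern.** A significance test asks whether the malignant and benign distributions of the ratio differ. A diagnostic objective asks how well the ratio tells one kind of tumor from the other. The first can be answered yes while the second is answered poorly or very imprecisely, and the plan provides only for the first.

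The logistic model does not close the gap. Its outcome, as 11.2 describes it, is tumor versus non-tumor tissue. Patients enter with a BI-RADS 4 or 5 lesion awaiting biopsy, so a lesion that proves benign is coded the same way as a cancer. The model could be significant because masses differ from the tissue around them, whatever their histology.

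At stake is what the pilot hands on. Whether to run a diagnostic study, and how large, depends on an estimate of discrimination and its uncertainty. If none is specified, a performance measure or cut-point may be chosen after the data are seen.

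**Working it through.** **1. The plan's own figure.** The only sample-size figure is 19 to 29 in 11.3, for the correlation (two-tailed 0.05, 80% power, r = 0.6 to 0.5). By Fisher z, n = ((1.960 + 0.842)/atanh(r))² + 3.
- r = 0.5: 7.849/0.3017 + 3 = 29.01
- r = 0.6: 7.849/0.4805 + 3 = 19.34

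The range reproduces to within rounding. There is no corresponding figure for malignancy.

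**2. Inputs for the secondary question.**
- From the documents: 25 patients (3.2), level 0.05 (2.2.2), Mann-Whitney or t-test (11.2).
- Assumed: one tumor per patient, a two-sided test (2.2.2 does not state sidedness), and a split between 6 malignant/19 benign and 15/10, because no malignant fraction is given.

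**3. Smallest AUC that reaches significance.** AUC = U/(m × n), with m malignant and n benign. The exact null distribution of U gives the smallest U with two-sided p ≤ 0.05. The standard error is Hanley-McNeil. The 95% interval is shown on the plain (Wald) and logit scales. The last column is sensitivity = specificity at the best cut-point under an equal-variance binormal model.

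| Malignant/benign | U/(mn) | AUC | p | Wald 95% CI | Logit 95% CI | Sens = spec |
|---|---|---|---|---|---|---|
| 6/19 | 89/114 | 0.781 | 0.043 | 0.54–1.02 | 0.47–0.93 | 0.71 |
| 8/17 | 102/136 | 0.750 | 0.050 | 0.53–0.97 | 0.48–0.91 | 0.68 |
| 10/15 | 111/150 | 0.740 | 0.048 | 0.53–0.95 | 0.49–0.89 | 0.68 |
| 12/13 | 115/156 | 0.737 | 0.046 | 0.54–0.94 | 0.50–0.89 | 0.67 |
| 15/10 | 111/150 | 0.740 | 0.048 | 0.55–0.93 | 0.51–0.89 | 0.68 |

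The 10/15 row in full:
- Q1 = 0.74/1.26 = 0.5873; Q2 = 2 × 0.5476/1.74 = 0.6294.
- SE² = [0.1924 + 9 × (0.5873 − 0.5476) + 14 × (0.6294 − 0.5476)]/150 = 0.0113, so SE = 0.106.
- Wald: 0.74 ± 1.96 × 0.106 = 0.53 to 0.95.
- Logit: ln(0.74/0.26) = 1.046 with SE 0.106/0.1924 = 0.55, which back-transforms to 0.49 to 0.89.
- Binormal separation d = √2 × z(0.74) = 0.91. Balanced accuracy is Φ(0.91/2) = 0.68. Sensitivity at 90% specificity is Φ(0.91 − 1.28) = 0.36.

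With the t-test at 10/15, the critical d is 2.069 × √(1/10 + 1/15) = 0.84, an AUC of Φ(0.84/√2) = 0.725. The choice of test hardly matters.

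**4. How often significance occurs.** Simulated Mann-Whitney power at 12/13 under the binormal model:

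| True AUC | P(p < 0.05) |
|---|---|
| 0.60 | 12% |
| 0.65 | 23% |
| 0.70 | 40% |
| 0.80 | 78% |

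When a true AUC of 0.65 does reach significance, the mean observed AUC is about 0.79. A bare statement of significance conceals how imprecise that estimate is.

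**The case against.** A reader might infer that p < 0.05 is the success criterion, so that a weak marker would be declared a predictor of malignancy. The documents do not support that. Section 2.2.2 sets a test level and no success rule. Section 2.2.1 shows that the authors knew how to write one, since they did so for the correlation (r above 0.5). The study is labelled a pilot, 11.2 words the logistic analysis as exploratory, and 1.4.2 says only that the work may lead to a predictor. A weak marker would also usually fail: a true AUC of 0.60 to 0.65 reaches significance in about 12% to 23% of trials.

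It can also be said that:
- 2.2.2 names logistic modeling, so the endpoint is not only a two-group test;
- the Study Summary asks whether SHAPE carries diagnostic information at all, and a Mann-Whitney test is a fair first answer to that;
- the imprecision comes from having 25 patients, and no change of endpoint removes it.

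Most of this stands, and it limits the point to what could be reported. It does not supply the missing estimate. The logistic model has the wrong outcome for malignancy, the wording in 2.1.2 goes beyond a test of any separation, and imprecision in a pilot is a reason to show an interval.

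**Conclusion.** The point holds in a limited form. The secondary objective concerns discrimination between malignant and benign tumors, and no analysis in the plan estimates it. A just-significant result could therefore be presented as prediction when the observed AUC is about 0.74 to 0.78, balanced accuracy at 0.74 is about 68%, and the 95% lower limit is about 0.47 to 0.55.

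These figures rest on the assumed splits, one tumor per patient, a two-sided test and, for balanced accuracy, a binormal model. The lower limit depends on the method: 0.53 to 0.55 by Wald, whose upper limit exceeds 1 at 6/19, and 0.47 to 0.51 on the logit scale. Neither range should be taken as firm. The documents do not show that a weak discriminator would be declared successful, and this is a secondary aim of a pilot. It is worth correcting because the correction is nearly free.

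**What to change.** In 2.2.2 and 11.2:

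- Define the secondary endpoint as the AUC of the tumor subharmonic ratio for malignant versus benign on biopsy, one tumor per patient, with a 95% confidence interval by a method named in advance (for example logit-scale or bootstrap).
- Keep the Mann-Whitney or t-test p-value as supportive.
- Fit any logistic model of malignancy to malignant versus benign among tumors. If tumor versus non-tumor is kept, present it as a separate question.
- Label the malignancy result exploratory.

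The cost is a few sentences and one further line of analysis on data already collected, since the AUC is U divided by the product of the two group sizes. The downside is that a wide interval becomes visible. The change does not raise power or reduce missed effects: at 12/13 a true AUC of 0.80 would still fail to reach significance about 22% of the time (100% − 78%).

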3.1 Characteristics

This is an open-label, non-randomized, human trial that will be conducted at one clinical site, Thomas Jefferson University. Before IFP measurement, all participants will have an unenhanced (baseline) ultrasound imaging study followed by CEUS imaging study with a single infusion of Definity. Then, they will have the IFP measurements taken by Stryker compartment pressure monitoring system from a breast tumor and its surrounding tissue with ultrasound imaging guide.

3.2 Number of Participants

We plan to enroll 25 participants.

3.3 Duration of Therapy

The total infusion of Definity will be about 15 minutes.

3.4 Duration of Follow Up

All participants will have a 30-minute monitoring period after the administration of Definity.

3.5 Study Timeline

The period of this study is 15 months and the primary and secondary studies will be completed at the same time.

Year 1

- (a) Begin enrolling patients (Quarter 1)
- (b) Active patient enrollment (Quarter 2-4)
- (c) 3D SHAPE data analysis (Quarter 2-4)

Year 2

- (a) Active patient enrollment (Quarter 5)
- (b) 3D SHAPE data analysis (Quarter 5)
- (c) Statistical analysis and preparation for publications (Quarter 5)

